Sample size/power. Our primary outcome variable is weekly gestational weight gain (GWG). A final sample size of 72 women (36 per group, after accounting for 20% attrition from the 90 enrolled) will have 80% power to detect a time-averaged between-group difference in weekly GWG with a medium effect size (standardized between-group difference of 0.6). This effect size is translated to a between-group difference of 0.33 lb in weekly GWG, assuming a common standard deviation of 0.55 lb (or 0.25 kg) based on previous research.²⁷ The power analysis was conducted using mixed-effect linear modeling with a two-sided significance level of 0.05, assuming a correlation of 0.7 between the two weekly GWG measures. Due to the pilot nature of the study, our sample size is not powered to detect smaller effect sizes (<0.6). Nevertheless, we will report point estimates, effect sizes, and 95% confidence intervals. These estimates along with clinical significance will guide the results interpretation and sample size determination for a future full-scale RCT (R01).

C. Measurement/ Instrumentation

All participants will be assessed at ≤ 16 week-gestation (T1), 24-27 week-gestation (T2) and 35-37 week-gestation (T3). Survey data will be collected online using password-protected security-ensured Research Electronic Data Capture (REDCap), a secure web application for building and managing online surveys and databases. Primary and secondary outcomes will be extracted from electronic health record. An incentive of \$40 will be provided for participation in each point of data collection for all measurements.

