Intervention group. Intervention participants will be asked to self-generate 3-5 text messages to remind them to complete the intervention activities and join brief individual coaching via zoom. Next, they will receive a link to complete part I intervention activities, which will take up to 30 minutes to complete. Participants will use their first and last name, and birthday and own device (e.g., smart phone) to log into the intervention website and complete activities, while the research staff still on Zoom to answer women's questions if they have. After completion of the Part I intervention activities, the research staff will schedule an individual coaching session via zoom with the trained interventionist within the next two days. Participants will be informed that each coaching session will be recorded (either audio or video per their preferences). The recording will be transcribed and be analyzed to help us revise the individual coaching sessions for future studies. We will send a zoom link to participants to join the individual coaching session.

Cohort retention. We will apply our previously successful retention strategies. The RA will make a monthly retention call to maintain relationships and ask for updated contact information and pregnancy status.. We will allow temporary lapses as needed (e.g., partial data collection) or extend the time window for data collection. We will monitor the retention rate monthly and keep retention logs by asking participants over the phone about their reasons for dropout and any adjustments that could keep them in the study.

Randomization. [name] (Co-I, biostatistician) will generate a randomization schedule. The Project Director will use the randomization schedule to randomize participants to an intervention or usual care group. Our randomization protocol will utilize a stratified permuted-block algorithm.^{121,122} Specifically, women in each race stratum (White vs. minority) will be randomly allocated 1:1 to intervention or usual care using permuted block randomization with varying block sizes of 2 or 4.

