Figure 2. Topics for the 20-week intervention. SM = stress management, HE = healthy eating. SM includes three subtopics (e.g., better ways to handle everyday life) and 13 short-term goals (e.g., have a better relationship with family). HE includes four subtopics (e.g., effective ways to reduce junk food intake) and 11 short-term goals (e.g., daily eat less junk food and be mindful what I eat). PA has one subtopic and three short-term goals (e.g., being more physically active outdoors). Our intervention has greater emphasis on SM and HE than PA, because stress impairs ExF⁵⁷ and affects dietary intake,^{88,128} which is a strong predictor of EGWG.²⁷

| | 1 | 2 | 3 | 4 | 5 | 6 | 7 | 8 | 9 | 10 | 11 | 12 | 13 | 14 | 15 | 16 | 17 | 18 | 19 | 20 |
|--|---|---|----|---|---|----|---|---|---|----|----|----|----|----|----|----|----|----|----|----|
| Weekly web (30-35 min/week) | S | H | PA | S | H | PA | H | S | H | H | S | H | PA | S | H | PA | H | S | H | H |
| Individual coaching via zoom (15 min/call, 10 calls) | X | X | X | X | | X | | X | | X | | X | | | | X | | | | X |

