E. Internal Validity

Feasibility of recruitment, retention, intervention adherence and acceptability (Aim 1). We already plan to track *recruitment and retention* activities. *Intervention adherence.* The web will track and capture details about all activities (e.g., number of logins and amount of and type of contents used). We will also ask intervention participants about motivation and barriers preventing them from using the web. *Acceptability.* We will assess acceptability by asking participants to evaluate the usefulness of with each intervention component, e.g., personal values, using 5 Ws and H, and rehearsal. Lessons learned and results of this aim will be used to refine our future R01, e.g., recruitment and intervention.

Measures (See above and File Name: Study Survey. shown above). [name] will use the NHANES anthropometric manual¹³⁴ to train the data collectors (unaware of participants' group assignment) on measuring BW until we reach inter-rater reliability of $\geq 95\%$. Self-reported data will be collected online using password-protected security-ensured Research Electronic Data Capture (REDCAP).

F. Statistical analysis

Statistical analysis-need to consistent with hypothesis. We will use descriptive statistics to examine variable distributions, check for outliers, and summarize sample characteristics. Bivariate tests (T-test and Chi-square) will be used to compare sample characteristics between the two study groups. Congruent with the RCT nature of the design, we will conduct intent-to-treat analysis. **Aim 1.** We will (1) conduct content analysis to analyze recruitment/enrollment, retention and intervention adherence logs to identify successful strategies used, (2) review quality of steps generated to achieve goals (using a scoring system), and (3) perform descriptive statistics. We will use the following criteria to determine feasibility: 30% of women screened will meet the study criteria and 8-9 women enroll monthly (recruitment); 75% of consented women will enroll (randomization); 80% women will have measured body weight at T3 (retention). Also, 85% of women will

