complete ≥ 12 weekly intervention activity with $\geq 80\%$ weekly activities completed; 75% of women will be able to generate good quality of steps to achieve their chosen goals; 80% will use the pre-written goals instead of type in (intervention implementation). **Aim 2**, we will first use descriptive statistics and trend plots to summarize and visually compare the weekly gestation weight gain over time. Mixed-effects linear modeling will be used to model the weekly GWG as a linear function of treatment (intervention vs. usual prenatal care care), time, and treatment by time interaction. From the model, we can derive estimates of the time-averaged weekly gestational weight gain for each group, the between-group difference in weekly gestational weight gain at each time point and adjust for within-subject clustering from repeated measures and covariates (e.g., race). We will use logistic regression to estimate the between-group (intervention vs. usual care) difference in the probability of having a binary outcome (for example, excessive gestational weight gain, gestational hypertension, new born body weight), adjusting for covariates (e.g., race). **Aims 3 and 4**, mixed-effects linear modeling will be used to model each continuous outcome (dietary intakes, PA, and psychological eating for Aim 3; motivation, emotion and cognition for Aim 4) as a linear function of treatment, time, and the treatment by time interaction. The intervention effects will be estimated by between-group comparisons of change in the outcome (e.g., healthy lifestyle behaviors) from baseline. Again, we will adjust for within-subject clustering from repeated measures and covariates (e.g., race) in the mixed-effects regression models. **Missing data**. We will carefully examine the pattern of missing data and conduct appropriate multiple imputation if missing at random is indicated. The mixed-effects modeling allows for missing at random. If missing not at random exists, pattern mixture modeling will be used. Sensitivity analysis will evaluate the robustness of study findings without multiple imputation vs. those with imputation or from pattern-mixture modeling.

Zoom IRB Boilerplate:

Zoom is a secure, user-friendly, cloud-based enterprise videoconferencing service that Ohio State University implemented in 2018. Zoom is accessible to faculty and staff at all Ohio State campuses via <https://carmenzoom.osu.edu> .

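### The Aim 3 models for steps and energy expenditure commit to no calendar term; if walking is seasonal, the reported intervals for steps are somewhat conservative, without bias

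*Combined protocol and SAP*

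**What the plan says.** Section F, Aims 3 and 4, models each continuous outcome on arm, visit and their interaction, and estimates the effect as the between-arm difference in change from baseline. On adjustment it states that "we will adjust for within-subject clustering from repeated measures and covariates (e.g., race) in the mixed-effects regression models". Race is the only covariate named. No season, month or date term appears anywhere in the document.

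Four other places set the timing and context:

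- **Accrual.** Section A sets enrolment at 90. The Aim 1 feasibility criteria in section F expect that "8-9 women enroll monthly (recruitment").
- **Visits.** T1 is at 15 weeks or earlier in section A and at 16 weeks or earlier in section C. Both put T2 at 24-27 weeks and T3 at 35-37 weeks. The two T1 limits should be reconciled, but the point here holds under either.
- **Setting and content.** Section B restricts entry to residents of one county. The note to Figure 2 gives "being more physically active outdoors" as an example of a short-term physical activity goal.
- **Allocation.** Section D randomizes 1:1 within race stratum, by "permuted block randomization with varying block sizes of 2 or 4".

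**The concern.** Time in the model means the visit, not the date. A visit effect removes what all women share between T1 and T3. A seasonal shift is not shared: a woman measured first in autumn and last in late winter moves one way, and a woman measured first in late winter and last in summer moves the other. With entry spread over most of a year, these shifts vary in sign and size, and anything seasonal is left in the residual.

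The randomization already balances entry date closely. Balancing a predictive factor in the design and then leaving it out of the analysis gives a reported standard error larger than the true one. The sample size paragraph in section B says that estimates and 95% intervals will guide the full-scale trial, so an avoidably wide interval, or an SD inflated by removable variation, would carry forward into planning for this outcome.

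**Working it through.** **1. The plan's own figure.** The only power statement concerns weekly weight gain: "A final sample size of 72 women (36 per group, after accounting for 20% attrition from the 90 enrolled) will have 80% power", for a "standardized between-group difference of 0.6". With two measures correlated 0.7, the SD of the average is 0.55 × √((1+0.7)/2) = 0.507 lb. The standard error is 0.507 × √(2/36) = 0.1195 and 0.33/0.1195 = 2.76. Power is therefore about Φ(2.76 − 1.96) = 0.788, close to the stated 80%. No power figure, SD or correlation is given for steps or energy expenditure, so the inputs in steps 4 to 6 are assumptions.

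**2. Timing.** Recruitment lasts 90/9 = 10.0 to 90/8 = 11.25 months if the feasibility target is met. T1 to T3 runs from 35 − 16 = 19 weeks (0.36 year) to 37 − 13 = 24 weeks (0.46 year). T1 has no lower limit; 13 weeks is the eligibility limit, used here as an early case. The central case, 15 to 36 weeks, is 21 weeks or 0.40 year. T1 to T2 is shorter, about 0.15 to 0.27 year.

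**3. Seasonal contrast.** Let A be half the peak-to-trough swing of a yearly sine wave. A change over L years has seasonal amplitude 2A·sin(πL), which at L = 0.40 is 1.90A against a maximum of 2A. Its variance over a full year of entry dates is 2A²·sin²(πL) = 1.81A². For a 10-month accrual it lies between about 1.4A² and 2.1A², depending on the starting month.

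**4. Reported interval width in the three-visit model.** Assume a random intercept, a non-seasonal SD of 2,500 or 3,000 steps/day, and a correlation between visits of 0.6 or 0.5. The non-seasonal within-woman variance is SD²(1 − r), which is 2.5 million or 4.5 million. With lags of 0.20, 0.20 and 0.40 year, the pairwise seasonal variances are 0.69A², 0.69A² and 1.81A². Their contribution to the pooled within-woman variance is one sixth of the sum: 3.19A²/6 = 0.53A². The width ratio is √(1 + 0.53A²/[SD²(1 − r)]).

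| Swing (steps/day) | A | Too wide, SD 2,500, r 0.6 | Too wide, SD 3,000, r 0.5 |
|---|---|---|---|
| 500 | 250 | 0.7% | 0.4% |
| 1,000 | 500 | 2.6% | 1.5% |
| 1,500 | 750 | 5.8% | 3.3% |
| 2,000 | 1,000 | 10.1% | 5.7% |

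The two added terms cost about 0.3% in standard error, so the net gain is slightly below each entry. Simulation of the three-visit random-intercept model agrees: about 0% up to 500 steps, 1-2% at 1,000, and about 6% at 1,500 and 10% at 2,000 for the first column.

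**5. Reported against true precision.** This was simulated on the T1-T3 change alone, with race-stratified blocks of 2 or 4 and 20% loss (all in steps/day):

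| A, SD | True SD of unadjusted arm difference | Its model SE | SE with season added |
|---|---|---|---|
| 500, 3,000 | 717 | 726 | 711 |
| 750, 2,500 | 536 | 579 | 530 |
| 1,000, 2,500 | 552 | 613 | 529 |

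The reported standard error rises while the true SD hardly moves. Adding season lowers the estimator's actual SD by about 0-4%. Coverage without the terms is 95.5-96.8% for swings of 1,000 to 2,000 steps.

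**6. T1 to T2.** The seasonal contrast is smaller: 2·sin(πL) is 0.93 at L = 0.153 and 1.49 at L = 0.268, against 1.90 at 0.40. That change analysed alone is affected less. Under a random intercept with one residual variance, its reported interval would still carry the pooled inflation.

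**The case against.** The strongest objection is that the effect may not exist. No section gives a seasonal amplitude for walking. The textual hook is one example goal about the outdoors, and the note to Figure 2 says that physical activity receives less emphasis than the other topics. This stands: the size is conditional, and below a swing of about 500 steps/day there is nothing to gain.

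The covariate list is also open, so the plan does not exclude a calendar term. That stands too; the point is only that none is committed to. Other predictors of steps, such as wear time, could claim a place. That does not count against a date term.

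Third, steps are an unpowered outcome in a pilot, and the error is conservative. That limits the importance but does not remove the benefit.

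A reader might infer that season confounds the arm comparison. The blocks of 2 or 4 speak against it: entry dates are balanced, and simulation showed no bias. A reader might also infer that much of the trial's information on walking is lost. The small change in the true SD speaks against that; what is inflated is mainly the reported standard error.

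Last, T2 and T3 wear dates follow randomization, and section D lets collection windows be extended. The dates are set mainly by entry date and gestational age, and a shift of a few weeks changes an annual cycle little.

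**Conclusion.** The point holds as a minor improvement. The plan commits to no calendar term for the device-measured outcomes, and the visit spacing and accrual would leave any seasonal swing in the residual. For steps, the reported intervals would be too wide by about 0% up to a 500-step swing, 1-2% at 1,000, about 3-6% at 1,500 and about 6-10% at 2,000. In each range the larger figure belongs to an SD of 2,500 with correlation 0.6, the smaller to 3,000 with 0.5. True precision lost is about 0-4%. There is no bias, and the error is in the conservative direction.

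These sizes rest on an assumed yearly sine wave, an assumed SD and correlation, a random-intercept model, and accrual at the target rate. Nothing was computed for energy expenditure, so for that outcome only the mechanism is argued. The documents do not support saying that the intervals are certainly too wide.

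**What to change.** Add one sentence to section F, Aim 3: the mixed models for steps and for energy expenditure will include, as fixed effects beside race, one sine and one cosine term with a 12-month period, evaluated at the calendar date of each Actigraph recording (for example, the midpoint of the wear period), with coefficients common to both arms.

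No new data should be needed, since each recording has a date. The cost is two degrees of freedom, about 0.3% in standard error if walking is not seasonal. If seasonality is small, the gain is negligible. Fixing the terms in advance avoids choosing them after the data are seen.
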